4. ANALYSIS SETS (POPULATIONS FOR ANALYSIS)

For purposes of analysis, the following analysis sets are defined:

Note that participants randomized at sites terminated by the Sponsor for Good Clinical Practice (GC) non-compliance will not have their data included in any summary outputs or analyses (i.e. they will be excluded from the Evaluable and Safety Analysis Sets), but their data will be retained in listings as part of the All Randomized Participants set below.

Table 8. Analysis Set Definitions

Participants Analysis Set	Description		
Enrolled	All participants who sign the ICD and are enrolled into the Main study		
Randomly assigned to investigational product	All randomized participants		
Evaluable (i.e. Full Analysis	Defined according to the Full Analysis Set:		
Set)	All randomized participants who take at least 1 dose of investigational product who have provided baseline data for the primary endpoint (i.e. evaluable baseline biopsy data). Participants will be analyzed according to the treatment group they are randomized to.		
	 The only exception to this is for participants randomized before Protocol Amendment 1 is enacted who are randomized to either of the 2 QD dosing regimens of DGAT2i alone, will be analyzed under the corresponding DGAT2i BID treatment group. 		
Safety	All participants who take at least 1 dose of investigational product. Participants will be analyzed according to the treatment they actually received.		
	 The only exception to this is for participants randomized before Protocol Amendment 1 is enacted who are randomized to either of 		

Table 8. Analysis Set Definitions

	the 2 QD dosing regimens of DGAT2i alone, will be analyzed under the corresponding DGAT2i BID treatment group.			
Defined Analysis Data Set (at the data level) – endpoint specific	Description			
All biopsy-derived endpoints				
Biopsy-based Composite Estimand	If a participant discontinues treatment or from the study due to lack of efficacy or toleration prior to Week 48 or if they do not have evaluable Week 48 Biopsy data, they will be considered to be a non-responder. If they withdraw from treatment for other reasons (not related to lack of efficacy or toleration) and have evaluable biopsy data at withdrawal or Week 48, these data will be utilized to determine whether they are a responder or not.			
Biopsy-based Composite Estimand for 'Worsening from Baseline' exploratory liver biopsy endpoints	If a participant discontinues treatment or from the study due to lack of efficacy or toleration prior to Week 48 or if they do not have evaluable Week 48 Biopsy data, they will be considered to be a responder. If a participant improves or remains the same compared to baseline, then that participant will be termed as a non-responder. If they withdraw from treatment for other reasons (not related to lack of efficacy or toleration) and have evaluable biopsy data at withdrawal or Week 48, these data will be utilized to determine whether they are a responder or not.			
Biopsy-based Hypothetical Estimand	Any available biopsy data for all participants collected before or at the time of treatment withdrawal will be included in the analysis, even if they have withdrawn from treatment for lack of efficacy or toleration. Endpoint data collected after treatment withdrawal will be censored. This analysis will be carried out under the assumption that missing data at Week 48 are missing at random conditional on dose and the strata formed by the covariates			
All MRI-PDFF-derived endpoints (in Imaging Substudy)				
MRI-based Hypothetical Estimand	Any available MRI data for all participants collected before or at the time of treatment withdrawal will be included in the analysis, even if they have withdrawn from treatment for lack of efficacy or toleration. Endpoint data collected after treatment withdrawal will be censored. Missing data at Week 48 will not be imputed. MMRM adjusted for covariates will be used to obtain LS mean estimate at Week 48 for each dose, which will then be used in fitting the Bayesian Emax model			

Data for all participants will be assessed to determine if participants meet the criteria for inclusion in each analysis population prior to unblinding and releasing the database and classifications will be documented per standard operating procedures.

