9.3. Analysis Sets

For purposes of analysis, the following analysis sets are defined:

Patients Analysis Set	Description	
Enrolled	All participants who sign the PreQ ICD	
Randomly assigned to investigational product	All randomized participants	
Evaluable	Defined according to the Full Analysis Set:	
	All randomized participants who take at least 1 dose of investigational product who have provided baseline data for the primary endpoint (i.e. baseline biopsy data). Participants will be analyzed according to the treatment group they are randomized to.	
	 The only exception to this is for participants randomized before Protocol Amendment 1 is enacted who are randomized to either of the 2 QD dosing regimens of DGAT2i alone, who switch to the corresponding BID dosing regimen of DGAT2i alone, and will be analyzed under that treatment group. 	
Safety	All randomized participants who take at least 1 dose of investigational product. Participants will be analyzed according to the treatment they actually received.	
	 The only exception to this is for participants randomized before Protocol Amendment 1 is enacted who are randomized to either of the 2 QD dosing regimens of DGAT2i alone, who switch to the corresponding BID dosing regimen of DGAT2i alone, and will be analyzed under that treatment group. 	

Final Protocol Amendment 1, 30 August 2021

Defined Analysis Data Set (at the data level) – endpoint specific	Description		
All biopsy-derived endpoints			
Biopsy-based Composite Estimand	If a participant discontinues treatment or from the study due to lack of efficacy or toleration prior to Week 48 or if they do not have Week 48 Biopsy data, they will be considered to be a non-responder.		
Biopsy-based Hypothetical Estimand	Any available biopsy data for all participants collected before or at the time of treatment withdrawal will be included in the analysis, even if they have withdrawn from treatment for lack of efficacy or toleration. Endpoint data collected after treatment withdrawal will be censored.		
All MRI-PDFF-derived endpoints (in Imaging Substudy)			
MRI-based Hypothetical Estimand	Any available MRI data for all participants collected before or at the time of treatment withdrawal will be included in the analysis, even if they have withdrawn from treatment for lack of efficacy or toleration. Endpoint data collected after treatment withdrawal will be censored.		

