- Dose increase and separately decrease in concomitant lipid-modifying medications, i.e. medications for
 - HDL-C decreased
 - LDL-C increased
 - Triglycerides increased
 - The relevant data can be obtained from the CM001_2, 3 and 5 pages (Hypercholesterolemia category) from the eCRF.
- Dose increase and separately decrease in concomitant blood pressure management medications, i.e. medications for
 - Hypertension
 - The relevant data can be obtained from the CM001_4 pages (Anti-hypertension agents category) from the eCRF.
- Dose increase and separately decrease in concomitant therapies relating to:
 - Hypothyroidism
 - The relevant data can be obtained from the CM001_6 pages (Hypothyroidism medications category) from the eCRF.

To assess for changes in alcohol consumption during the study, changes from baseline in the Alcohol use disorders identification test (AUDIT) questionnaire total score and the Absolute Value in Percent carbohydrate deficient transferrin relative to total transferrin (%CDT), will also be summarized descriptively over time.

Drug-Induced Liver Injury (DILI) and Hy's Law Criteria

A summary table will categorize the number and percentage of participants in each treatment group who meet the criteria, defined differently for participants with Normal baseline

and Abnormal baseline (see Appendix 6 of protocol for definition of potential Hy's Law and Potential DILI)

Participants meeting the AST/ALT and TBili criteria will be categorized as potential Hy's Law cases, and participants who meet the AST/ALT criteria but not the TBili criteria will be categorized as potential DILI cases.

eDish plots will be produced (Peak ALT vs Peak TBili and Peak AST vs Peak TBili), with sectors delineated by the following lines to indicate elevations in ALT, AST and TBili:

- two vertical lines at the point at which Peak ALT (or AST) = 3 x ULN and at 8 x ULN
- a horizontal line at the point at which Peak Total Bilirubin = 1 x ULN and at 2 x ULN

Separate plots will be produced for each treatment group, with males and females identified using different symbols.

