6.3.7. Event-based Tertiary/Exploratory Endpoints

6.3.7.1. Main Analysis

The following endpoints will be summarized descriptively by treatment group (Section 5.2.4) for randomized participants, separately for pre-randomization events and treatment-emergent events (as SAEs will be collected prior to randomization so could also be sent for adjudication):

 Occurrence of any one of the following over time up to Week 48 based on final adjudication:

Deaths

- All cause mortality (deaths regardless of cause)
- Death due to Myocardial Infarction
- Death due to Cerebrovascular Accident
- Death due to Hepatic failure

For non-fatal events.

- Cardiovascular events
 - Myocardial infarction

- Cerebrovascular event (stroke) or transient ischaemic attack
- Hospitalizations due to unstable angina
- Hospitalization for heart failure

Liver events

- Hepatic encephalopathy
- Upper Gastrointestinal bleed due to portal hypertension
- Liver transplant evaluation
- New diagnosis of hepatocellular carcinoma
- Ascites
- Acute kidney injury due to hepatorenal syndrome
- Drug induced liver injury
- Increase of Model of end-stage liver disease (MELD) score from ≤12 to ≥15 indicating listing for liver transplant (See Appendix 2.4.2)

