6.6. Safety Summaries and Analyses

All safety analyses will be performed on the safety population. These will be presented in tabular and/or graphical format and summarized descriptively and will follow Pfizer standards as appropriate. Further details are provided below.

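### Dosed participants at sites closed for GCP non-compliance are left out of every planned by-arm safety summary and appear only in listings; a short summary of serious outcomes in all dosed participants should be added.

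*SAP*

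**What the plan says.** The note above SAP Table 8 deals with participants randomised at sites that the sponsor terminated for GCP non-compliance. They "will not have their data included in any summary outputs or analyses (i.e. they will be excluded from the Evaluable and Safety Analysis Sets"). The sentence then limits this by keeping the records of these participants in the listings.

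The set definitions carry no such carve-out. Protocol 9.3 defines the Safety set as "All randomized participants who take at least 1 dose of investigational product. Participants will be analyzed according to the treatment they actually received". The Safety row of SAP Table 8 begins "All participants who take at least 1 dose of investigational product".

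Three other parts of the SAP bear on how far the note reaches:

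- SAP 6.6: "All safety analyses will be performed on the safety population".
- SAP 3.5.3, on drug-induced liver injury and Hy's law: "A summary table will categorize the number and percentage of participants in each treatment group who meet the criteria".
- SAP 6.3.7.1, on adjudicated deaths and cardiovascular and liver events: "The following endpoints will be summarized descriptively by treatment group (Section 5.2.4) for randomized participants".

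SAP 4.1 keeps people who were treated without being randomised in all safety analyses, under the regimen they received. On timing, SAP 4 says: "Data for all participants will be assessed to determine if participants meet the criteria for inclusion in each analysis population prior to unblinding".

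**The concern.** A Safety set normally follows exposure: whoever took the drug is counted. The note replaces exposure with a sponsor decision about site conduct, which may come after dosing and after an event. A participant treated without randomisation stays in the safety analyses, while one properly randomised and dosed at a site later closed does not.

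The note also sits badly with the text around it. A programmer working from Table 8 alone would build a larger Safety set than one who applies the note. SAP 6.3.7 refers to randomised participants, which would include closed sites, while the note bars their data from any summary.

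The stake is the final by-arm picture of rare, serious outcomes. This is the first study of these agents in biopsy-confirmed NASH with F2-F3 fibrosis, dosing runs to 48 weeks, and arms are planned at about 50. At that size one or two events change what a table shows. Listings preserve the record but give no counts, denominators or comparison by arm, and no safety summary that includes these participants is planned.

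**Working it through.** The plan gives no figure to reproduce. The check is a comparison of text, followed by an illustration on assumed numbers.

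**Reach of the note**

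- *Adverse events, laboratory data, vital signs, ECGs (SAP 6.6).* These use the Safety set, so the note applies directly. Sections 6.6 to 6.6.4 name no separate tables of deaths, SAEs or discontinuations due to adverse events. Any produced under the sponsor's standards would inherit the same set.
- *Potential DILI and Hy's law (SAP 3.5.3).* This is a summary table by arm, so the ban on summary outputs covers it.
- *Adjudicated deaths, cardiovascular and liver events (SAP 6.3.7).* The stated population is randomised participants, but this is still a summary output. The two instructions conflict; the note's broad wording probably prevails, but the SAP does not say so.

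**Chance that an affected participant is dropped**

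Inputs: about 350 randomised, 50 per arm (SAP 2.2). The number of excluded dosed participants, k, and the event risk, p, are assumptions. Formula: P = 1 − (1 − p)^k.

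- With p = 2%: k = 7 (2% of 350) gives 1 − 0.98^7 = 13%; k = 14 (4%) gives 25%; k = 21 (6%) gives 35%.
- With k = 5: 5% at p = 1% and 23% at p = 5%. With k = 20: 18% and 64%. With k = 35: 30% and 83%.

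These figures pool all seven arms, placebo included. Spread evenly, 7, 14 or 21 exclusions are 1, 2 or 3 per arm. At p = 2%, the chance for one given arm is then 2.0%, 1 − 0.98² = 4.0%, or 1 − 0.98³ = 5.9%.

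**Precision when no event is seen**

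The exact one-sided 95% upper bound is 1 − 0.05^(1/n): 5.8% for n = 50, 6.4% for n = 45, 7.2% for n = 40.

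**Direction of the effect**

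- Dropping one affected participant: 2/50 = 4.0% becomes 1/49 = 2.0%.
- Dropping two event-free participants: 2/50 = 4.0% becomes 2/48 = 4.2%.
- Dropping the only placebo event: 2/50 versus 1/50 is a difference of 2.0 points; 2/50 versus 0/49 is 4.0 points.

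The count can only fall. The rate and the contrast can go either way.

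**Tier 2 threshold (SAP 6.6.1: at least 4 participants in any arm)**

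Take an event outside Tier 1 that reaches the threshold in one arm only. Losing one of four cases moves it to Tier 3, and the planned risk difference and interval disappear. For scale, the Miettinen-Nurminen score 95% interval is 0.5% to 18.9% for 4/50 versus 0/50, and −1.3% to 16.6% for 3/49 versus 0/50.

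**The case against.** The sponsor has a fair case, and much of it stands.

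- **The SAP may depart from the protocol.** Protocol Section 9 and SAP Section 2 allow this, and only major changes to the primary endpoint definition or its analysis must also go into an amendment. The note is an express rule. It is a choice of analysis set, not a breach.
- **Data from such sites may be unreliable, possibly including exposure itself.** SAP 6.3.8 allows placebo samples to be analysed for drug and listed where a site has quality problems. That suggests, without proving, that who took what may be in doubt. Including poor records can also distort safety rates.
- **Selective exclusion is limited.** Set membership is settled before unblinding.
- **Oversight runs separately.** SAEs go to the sponsor within 24 hours (Protocol 8.3.1.1), potential Hy's law cases are reported as SAEs (Protocol Appendix 6), and an independent committee adjudicates fatal, hepatic and cardiovascular events (Protocol 9.6). E-DMC outputs are defined in its charter or a separate interim plan (SAP 7.2).

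A reader might go further and infer that the protocol forbids any site exclusion, because it names the once-daily to twice-daily regrouping as the sole exception. It does not: that sentence qualifies the treatment group under which participants are analysed, not who belongs to the set. A reader might also infer that serious events are concealed. The listings and the separate reporting routes do not support that.

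What the objection leaves untouched is the final by-arm safety summary. Doubt about routine data does not make a death or an abnormal central laboratory result irrelevant, and none of these safeguards puts the event back into a table with a denominator.

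**Conclusion.** The point holds as a gap in the final safety summaries and as an unresolved conflict between the note, Table 8 and SAP 6.3.7. It is a cheap improvement, not a fault that undermines the trial.

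Its size is unknown. The documents do not state whether any site was closed or how many dosed participants it had. The 13% to 35% range assumes 7 to 21 exclusions, 2% risk and independent events, pooled over all arms; with even spread, the chance for a single arm is 2% to 6%. A reader might infer that the exclusion always flatters the drug. Only the fall in event counts is certain; losing placebo events or event-free participants can make an active arm look worse.

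Restoring every dosed participant to all safety tables is debatable, given the possible unreliability of the data. A summary of the serious outcomes that includes them is easier to justify.

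**What to change.** - Keep the GCP exclusion for the Evaluable set and, if wanted, for routine safety tables.
- Report the number of dosed participants excluded per arm.
- Add by-arm summaries, covering all dosed participants, of deaths, SAEs, adverse events leading to discontinuation, adjudicated events and potential DILI or Hy's law cases.
- Reword the note, the Safety row of Table 8 and SAP 6.3.7 so that they give one instruction on who is counted where.

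The cost is SAP wording and a few extra tables. The drawback is that those tables will contain some less reliable records, which a footnote can identify.

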Beyond the assessment on histological endpoints, the current study also undertakes assessment for potential improvement on non-invasive biomarkers – both imaging and blood-based. Assessment of liver fat and liver stiffness using ultrasound-based FibroScan® in the entire population and liver fat via the validated tool for clinical assessment of hepatic steatosis 7 - MRI-PDFF (in Imaging Substudy) is planned. The blood-based parameters include markers of liver function tests (ALT, AST, Alkaline phosphatase, GGT, Total bilirubin), NASH-related biomarkers 1 (3-parameter derived ELF 1 Score, marker of liver fibrosis used to track disease progression; CK18-M30 and CK18-M65, markers of apoptotic activity, ProC3, a marker of fibrinogenesis; ProC6, a marker of fibrinolysis), glycemic parameters (HbA1C, FPG, FPI, HOMA-IR, adiponectin), and fasting lipid parameters/markers of target engagement (total cholesterol, triglycerides, direct LDL-C, HDL-C, direct VLDL, apolipoprotein A1, Btotal, B100, B48, C3, and E plus PCSK9, hs-CRP).

Furthermore, recent research has indicated that there is an unrecognized symptom burden with NASH. In particular, abdominal pain, and fatigue, were identified as relevant in sponsor-conducted patient interviews and found to be responsive to histological change in a trial with obeticholic acid. ²² Inclusion of ePROs in the current study will allow testing of this hypothesis, and optimization of ePROs taken forward into Phase 3. Such data may also be valuable in supporting histology as a surrogate outcome in future health technology assessments. In this study, baseline, when obtained will be done at Visit 4/Baseline or while participants are receiving single-blind placebo – refer to Table 4.

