2.2. Study Design

The detailed set-up of the study is summarized below -

Figure 1. Study Design

This is a multicenter, multinational, randomized, double-blind, double-dummy, placebo-controlled, parallel-group, evaluation of DGAT2i alone, and DGAT2i+ACCi. Approximately 350 participants (50 per arm) with biopsy confirmed NASH with F2-F3 fibrosis, as assessed by sponsor-identified central pathologist(s), will be randomly assigned to the study intervention to ensure approximately 280 evaluable participants (40 per arm) offer evaluable data for the primary objective.

Participants will be randomized in a balanced ratio, using a computer-generated randomization code, to receive either double-blind, double-dummy placebo, 1 of 4 doses/dosing regimens of DGAT2i alone, or 1 of 2 dose-levels of DGAT2i+ACCi for a treatment duration of up to 48-weeks.

For participants randomized before Protocol Amendment 1 is enacted, those randomized to either of the 2 QD (DGAT2i 150 mg QD and DGAT2i 300 mg QD) dosing regimens of DGAT2i alone will remain in the study but will be switched to the corresponding BID dosing regimen of DGAT2i alone, maintaining the assigned total daily dose and the double-blind, double-dummy design. New randomization to the QD treatment arms will cease, after Health Authority (where applicable) and IRB/EC approvals of Protocol Amendment 1. Therefore, following Protocol Amendment 1, participants will be randomized to one of the following treatment arms:

Placebo

DGAT2i (Ervogastat) BID dose arms (for characterization of dose-response):

- DGAT2i 25 mg BID, total daily dose of 50 mg
- DGAT2i 75 mg BID, total daily dose of 150 mg
- DGAT2i 150 mg BID, total daily dose of 300 mg
- DGAT2i 300 mg BID, total daily dose of 600 mg

DGAT2i (Ervogastat) + ACCi (Clesacostat) coadministration dose arms:

- DGAT2i 150 mg BID + ACCi 5 mg BID
- DGAT2i 300 mg BID + ACCi 10 mg BID

The treatment group labels in programmed outputs will be as follows:

Placebo	PF-5571	PF-5571	PF-5571	PF-5571	PF-5571	PF-5571	Tota1
	25 mg	75 mg	150 mg	150 mg	300 mg	300 mg	
	BID	BID	BID	BID+	BID	BID+	
				PF1304 5		PF1304 10	
				mg BID		mg BID	

Following footnote to be included on all tables: PF5571 = Ervogastat and PF1304 = Clesacostat Note: A 'Total' column is required when summarizing baseline of population randomized

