The DGAT2i ED₅₀ for the histological-based primary endpoint has been assumed to be slightly higher than the projected EC₅₀ for reduction in liver fat which was estimated from a preliminary population pharmacokinetic model based on previous clinical studies with DGAT2i. Therefore, the DGAT2i ED₅₀ was estimated to be approximately 30 mg BID (TDD = 60 mg). The substantial uncertainty in ED₅₀ values was assessed in the meta-analyses of clinical dose response studies (Thomas, 2014). Therefore, based on the meta-analyses, a scaled t-distribution (with 5 degrees of freedom) is planned to be used that is focused on the initial projected ED₅₀=30 mg BID, with a scale parameter of 0.6. A normal prior distribution for the logit of the placebo response centered at logit(0.16) with a prior standard deviation of 2.0 (logistic scale) is planned to be used, which yields a weak diffuse prior distribution for the placebo response. A normal prior distribution for the Emax parameter will also be used, centred on the anticipated Emax (0.6) on the logistic scale. This prior distribution will also be diffuse on the logistic scale with a prior standard deviation of 2.0.

The proportion of primary endpoint responders in each treatment group will be analyzed by fitting a Bayesian Emax model to the data to characterize the dose response across all treatment groups and to estimate the proportion of responders (and 90% credible interval) for each dose studied, and to estimate the placebo-adjusted proportion of responders for each dose (and 90% credible interval). If an Emax model cannot be fitted to the data, then other models that allow dose response to be estimated will be fitted, i.e. linear, log-linear or exponential.

Note that a similar methodology will be used for the exploratory 'worsening from baseline' liver biopsy endpoints, but for this Estimand 3.1 will be utilized.

Pairwise Treatment Comparisons

The comparison of the proportion of responders for binary responder endpoints for DGAT2i BID doses vs placebo, and DGAT2i+ACCi BID doses vs placebo and corresponding DGAT2i BID monotherapy doses will be analyzed using logistic regression models, including baseline (SCR2 Eligibility) fibrosis stage (F2/F3) as a factor, to estimate the

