5.3. Methods to Manage Missing Data

For composite estimands, if a participant discontinues treatment or from the study due to lack of efficacy or toleration prior to Week 48 or if they do not have any evaluable Week 48 Biopsy data, they will be considered to be a non-responder (i.e. response will be imputed as 'non-response'). If they withdraw from the study for other reasons (not related to lack of efficacy or toleration) and have evaluable biopsy data at withdrawal or Week 48, these data will be utilized to determine whether they are a responder or not.

For hypothetical estimands, for the biopsy responder endpoints, analysis will be carried out under the assumption that missing data at Week 48 are missing at random conditional on dose and the strata formed by the covariates., The unconditional estimate of treatment effect will be obtained through covariate adjustment (ie, averaged over strata formed by baseline fibrosis status (F2/F3) and metabolic status (with or without T2DM)). For the continuous endpoint (i.e. percentage change from baseline in liver fat), missing data at Week 48 will not be imputed. MMRM adjusted for covariates will be used to obtain LS mean estimate at Week 48 for each dose, which will then be used in fitting the Bayesian Emax model.

For quantitative biopsy analyses, if the SCR2 Change from Baseline biopsy assessment is deemed to be 'Non-evaluable' the SCR2 Eligibility biopsy assessment will be used instead. If the Week 48 Change from Baseline biopsy assessment is deemed to be 'Non-evaluable', the Week 48 IPV biopsy assessment will be used instead (if this is available, as not all participants had a Week 48 IPV assessment).

Table 10. Handling non-evaluable histological change-from-baseline data

Scenario	Handling
CFB-SCR = nonevaluable (for NAS or fibrosis component(s) required for endpoint)	 Utilize SCR2 eligibility results for whichever component(s) is/are nonevaluable (ie, consensus results if available); if only parallel is available, select results from pathologists that had both the lowest NAS score and/or lowest fibrosis stage Qualitative assessment will only include data from whichever component is evaluable, if any (either NAS components or fibrosis)

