9. APPENDICES

Appendix 1. Summary of Efficacy Analyses

Endpoint	Analysis Type	Population	Data Inclusion and Rules for Handling Intercurrent Events and Missing Data	Analysis Model
Primary: Proportion of participants achieving	Summary	Evaluable	Observed data.	N/A
participants achieving centrally adjudicated resolution of NASH without worsening of fibrosis or improvement in fibrosis by ≥1 stage without worsening of NASH, or both, at Week 48	Main analysis (Estimand 1.1)	Evaluable	Participants who discontinue treatment or from the study due to lack of efficacy or toleration prior to Week 48 or if they do not have evaluable Week 48 Biopsy data, will be considered to be non-responders. All data collected at or after withdrawal from treatment for other reasons (not related to lack of efficacy or toleration) will be included.	Bayesian Emax for DR, Logistic Regression for pairwise comparisons
	Sensitivity Analyses	Evaluable	Same as main analysis, but may utilize alternative prior distributions for Bayesian Emax modelling.	Bayesian Emax for DR
	Supplementary analysis (Estimand 1.2)	Evaluable	All data collected before or at the time of treatment withdrawal will be included. Endpoint data collected after treatment withdrawal will be censored. Analysis will be	Bayesian Emax for DR, Logistic Regression for pairwise comparisons

Endpoint	Analysis Type	Population	Data Inclusion and Rules for Handling Intercurrent Events and Missing Data	Analysis Model
			carried out under the assumption that missing biopsies at Week 48 are missing at random conditional on dose and the strata formed by the covariates (fibrosis status and T2DM status).	
Secondary: Proportion of participants achieving	Summary	Evaluable	Observed data.	N/A
centrally adjudicated resolution of NASH without worsening of fibrosis at Week 48	Main analysis (Estimand 2.1)	Evaluable	Participants who discontinue treatment or from the study due to lack of efficacy or toleration prior to Week 48 or if they do not have evaluable Week 48 Biopsy data, will be considered to be non-responders. All data collected at or after withdrawal from treatment for other reasons (not related to lack of efficacy or toleration) will be included.	Bayesian Emax for DR, Logistic Regression for pairwise comparisons
	Sensitivity Analyses	Evaluable	Same as main analysis, but may utilize alternative prior distributions for Bayesian Emax modelling.	Bayesian Emax for DR

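### Estimand 1.2 treats missing Week 48 biopsies as random given only dose, fibrosis stage and T2DM, and leaves out the liver markers collected on treatment before withdrawal

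*SAP*

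**What the plan says.** SAP Table 8 (Biopsy-based Hypothetical Estimand) keeps biopsies taken up to or at treatment withdrawal, censors later ones, and then assumes that "missing data at Week 48 are missing at random conditional on dose and the strata formed by the covariates". Section 5.3 and Appendix 1 repeat the assumption and name two baseline covariates: fibrosis status and T2DM status. Section 5.3 averages the treatment effect over the strata that they form. No post-baseline variable is mentioned.

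For the other hypothetical estimand (2.5, liver fat by MRI-PDFF), Table 8 says "MMRM adjusted for covariates will be used to obtain LS mean estimate at Week 48 for each dose", so earlier on-treatment visits inform the dose-response input there.

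The sample-size text randomises 350 participants (50 per arm) to "ensure approximately 280 evaluable participants (40 per arm) offer evaluable data for the primary objective".

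The protocol's schedule of activities has chemistry at Weeks 2, 4, 6, 8, 12, 16, 24, 32, 40 and 48, and FibroScan at Weeks 6, 12, 24, 32, 40 and 48. Protocol 4.2 plans FibroScan for all participants. Under protocol 8.1.1, a biopsy at the decision to stop is taken only if at least 24 weeks have passed since Day 1.

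The sensitivity analyses named for the primary endpoint (SAP 6.1.1.2) vary the priors and are optional. None varies the missing-data assumption.

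**The concern.** Within a dose and an F2/F3-by-T2DM stratum, the assumption gives a participant without a biopsy the response rate of those with one. Someone whose ALT and CAP had not moved by Week 16, and someone whose markers were falling when a laboratory threshold ended treatment, are both treated as average members of their stratum.

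Some of this missingness is created by rule. Anyone who stops before Week 24 has no biopsy at stopping, and a Week 48 biopsy off treatment is censored, so they are always missing in Estimand 1.2. Many of them will have ALT values and at least a Week 6 FibroScan.

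The omitted markers are plausibly informative. Protocol 4.3 links changes in liver fat, ALT and AST to histological improvement. Missingness could also differ by arm: protocol 7.1 ties the triglyceride and platelet stopping thresholds to identified reactions to ACCi, which only the two combination arms receive.

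At stake is how far Estimand 1.2 can be trusted as a check on the composite result, in which missing biopsies count as non-response.

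**Working it through.** **The plan's own figures.** 280/350 = 40/50 = 0.80, so 20% are allowed to lack evaluable data. With placebo 16%, a 60% plateau and ED50 30 mg BID, the Emax model on the logit scale gives, at 150 mg BID, −1.658 + 2.064 × 150/180 = 0.062, which is 51.5%. The true difference from placebo is therefore 35.5 points. At n = 40 per arm its pairwise SE is √(0.16×0.84/40 + 0.515×0.485/40) = 9.8 points. The probability that the observed difference exceeds 24 points is Φ((35.5 − 24)/9.8) ≈ 0.88, or 0.91 at n = 50. This agrees with the stated 89%, so these rates are a fair reading of the design.

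**Bias formula.** In one arm, true rate = (1 − m) × observed-case rate + m × missing-case rate. Hence arm bias = m × (observed-case rate − missing-case rate), and contrast bias is the difference between the arm biases. At m = 0.20, a gap of 10, 20 or 30 points in one arm only gives 2, 4 or 6 points.

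**Assumptions not in the documents.** Within dose and stratum, a standard-normal on-treatment marker drives both response (AUC 0.68, 0.75 or 0.82) and missingness (log-odds slope up to 1.0 per SD), with 20% missing in each arm.

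**Worked case (AUC 0.75, slope 1.0, poor responders missing).**
- Active: observed 55.1%, missing 37.1%; 0.20 × 18.0 = +3.6 points.
- Placebo: observed 17.8%, missing 8.9%; 0.20 × 8.9 = +1.8 points.
- Same mechanism in both arms: 3.6 − 1.8 = +1.8. Active arm only: +3.6. Placebo only: −1.8.
- If good responders are missing on active (slope 0.5; observed 49.6%, missing 59.5%), the active-arm bias is 0.20 × (−9.9) = −2.0, and the contrast is −2.0 − 1.8 = −3.8.

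**Range over the assumed values, in points.**

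| Mechanism | 51.5% vs 16% | Combination vs monotherapy (true difference 6) |
|---|---|---|
| Same in both arms | +0.7 to +2.4 | about 0 |
| Active arm only (or one of the two active arms) | +2.1 to +4.6 | 2.0 to 4.6 either way |
| Placebo only | −1.1 to −2.2 | not applicable |
| Opposite directions | −2.9 to −4.8 | not run in this model |

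A second model has the marker normal with its mean shifted by 1.0 or 1.4 SD in responders, and slope 0.8. For 52% vs 16% it gives −1.6 to +2.8 with the same mechanism and 3.5 to 4.9 in size when only the active arm is affected. Opposite mechanisms give −5.2 to −7.0 there, and −6.9 to −9.5 for 58% vs 52%.

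**What conditioning on a marker recovers.** If the marker used is the one that drives missingness, the bias goes almost to zero, but that is close to true by construction. If it correlates only 0.5 with the driver, about 20 to 30% of a sizeable bias is removed (for example −5.2 becomes about −3.9, and −7.0 about −5.3). At 0.3, about 10% is removed. Root-mean-square error never rose by more than 0.1 point.

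**The case against.** Estimand 1.2 is supplementary. The main analysis does not use this assumption, and no hypothesis test or decision rule rests on it. Appendix 1 also plans an observed-data summary, so Estimand 1.2 is not the only view of the primary endpoint that avoids scoring missing biopsies as non-response. Biopsies at stopping from Week 24 on are kept, even after withdrawal for intolerance, and protocol 7.1 expects permanent discontinuation to be rare. Protocol 2.2 says it is unknown whether an effect on liver fat carries over to histology, and because the drugs lower liver fat directly, the marker-histology relation may differ by arm. The parallel with Estimand 2.5 is loose: biopsy has one post-baseline value, and the pairwise comparisons for 2.5 use a Week 48 ANCOVA. At n = 40 the pairwise SE is 9.8 to 11.1 points, larger than most of these biases.

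All of this stands and limits the weight of the point. It does not show that the stratum-only assumption is adequate for early stops, or that the missing-data assumption is tested anywhere.

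A reader might infer more: that the primary result is compromised, that bias of 5 to 9 points is to be expected, or that imputation would remove it. The documents support none of these. Estimand 1.1 handles missing biopsies differently. With 20% missing in each arm, biases above 5 points appeared only with opposite mechanisms in the two arms being compared. Near-complete removal assumes that the true driver of missingness is observed.

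**Conclusion.** The point holds as a limited one. Estimand 1.2 conditions on dose and two baseline factors, and sets aside on-treatment liver markers that the trial already collects. It is weakest for participants who stop before Week 24. At 20% missing, marker-driven missingness biases a responder difference by about 0 to 3 points if the arms share the mechanism, and by about 2 to 5 points if it acts in one arm only (placebo-only cases lie at the low end, 1 to 2 points). The bias is larger only if the mechanisms run in opposite directions. Against the 6-point combination effect used in the design, a one-arm mechanism is not negligible.

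These sizes rest on assumed marker strength and missingness slopes. The documents give no arm-specific drop-out and no marker-response association. The 20% is the plan's overall allowance, and the share missing under Estimand 1.2 could be higher (later biopsies censored) or lower (biopsies at stopping kept).

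**What to change.** In SAP Table 8, section 5.3 and Appendix 1, pre-specify for Estimand 1.2 a multiple-imputation analysis of responder status given treatment arm, fibrosis stage, T2DM, baseline NAS, and on-treatment change in ALT, CAP and VCTE up to the last visit at or before treatment withdrawal. Specify:
- how participants with no on-treatment marker are imputed (for example from arm and baseline variables alone);
- that baseline NAS is the SCR2 eligibility read, since the paired read exists only for those with an on-treatment biopsy, with a rule for when the two pathologists differ;
- whether the marker-response relation may differ by arm.

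Fit the planned Emax and logistic models to each completed data set. Pool posterior draws for Emax and use Rubin's rules for the logistic model. Report the result beside the present stratum-only version.

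The same edit should settle a related mismatch: the pairwise logistic model in SAP 5.2.1 is described as "including baseline (SCR2 Eligibility) fibrosis stage (F2/F3) as a factor", without T2DM, while section 5.3 conditions on both.

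The cost is SAP wording and one imputation program, with no new data, visits or participants. The model must be fixed before unblinding, and it corrects only the bias that the markers explain.
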